In clinical studies, 1.1% of 1024 evaluable patients tested positive for binding antibodies against ipilimumab in an electrochemiluminescent (ECL) based assay. This assay has substantial limitations in detecting anti-ipilimumab antibodies in the presence of ipilimumab. Infusion-related or peri-infusional reactions consistent with hypersensitivity or anaphylaxis were not reported in these 11 patients nor were neutralizing antibodies against ipilimumab detected. Because trough levels of ipilimumab interfere with the ECL assay results, a subset analysis was performed in the dose cohort with the lowest trough levels. In this analysis, 6.9% of 58 evaluable patients, who were treated with 0.3 mg/kg dose, tested positive for binding antibodies against ipilimumab. These results are highly dependent on methodology, and comparison of incidence of antibodies to ipilimumab with the incidences of antibodies to other products may be misleading.

Study Results and Clinical Efficacy

The clinical efficacy of ipilimumab as a single agent at a dose of 3 mg/kg administered q3w for 4 doses has been established in MDX010-20 (a randomized, controlled study in second line, locally advanced/metastatic melanoma), which led to approval of ipilimumab by the FDA. In study CA184024, the addition of 10 mg/kg ipilimumab to dacarbazine led to a prolongation of overall survival in patients with previously untreated melanoma.

In melanoma studies, disease stabilization in subjects receiving ipilimumab is characteristic of anti-tumor activity. Stable disease, sometimes of long duration, or slow steady decline of tumor lesion size over long periods of time, has been observed. Some subjects demonstrate initial tumor volume increase before response, possibly due to T-cell infiltration as shown by biopsies or to the time required for immunologic activation. Consequently, an initial determination of progressive disease and consequently PFS may not capture all patterns response and may underestimate the clinical activity of ipilimumab. Please see section “Considerations for Using Immune-Related Tumor Assessment Criteria (irRC).”

MDX010-20 (Phase 3, 3 mg/kg, previously treated melanoma)

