On a protocol by protocol basis, we would consider allowing study treatment to continue during initial progression up to the 12-16 week assessment to allow time for responses to be observed, if the patient is clinically stable, there is no deterioration in PS, and there is no need for immediate additional treatment. While maintaining standard definitions of progression and response, we would allow new lesions and some progression beyond 20% increases in tumor measurements during the initial treatment period to allow time for responses to develop (these delayed tumor responses may be seen in 10-20% of melanoma patients who initially progress during the initial treatment cycles and evaluation). We do not have experience with response patterns with combination therapy nor in diseases other than melanoma. Please use standard response definitions as the primary end point in these studies.

Note that the proposed irRC may be incorporated as secondary end points to compare to standard criteria and evaluate alternative patterns of response in various disease setting and treatment regimens.

Patients who demonstrate mixed responses, stable disease, or objective responses by standard RECIST following initial progression may be identified separately as “delayed SD, PR, or CR”.

Overall Risk/Benefit Assessment

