- The DLT window will be the first 8 weeks of combination treatment with decitabine and ipilimumab (starting day 1 of cycle 1).
- At the time of response assessments, patients with evidence of disease progression will come off study unless they have evidence of treatment tolerability and clinical benefit (i.e. improvement in transfusion frequency or peripheral blast reduction or symptom improvement). Patients with evidence of disease progression may be allowed to stay on study if deriving clinical benefit with approval from the overall PI as there may be a delayed response with

- immunotherapy.
- Patients with stable disease or better at the end of cycle 4 will move forward with treatment in the maintenance phase.
- **Cycles 5-12: Maintenance phase with combination decitabine and ipilimumab**
 - Pre-treatment Criteria
 - In the absence of disease, patients should have an absolute neutrophil count $\geq 500 \times 10^9/L$ or platelet count to $\geq 25,000 \times 10^9/L$ to proceed with each cycle. Dose delay recommendations are provided in section 6.
 - If there is still disease (partial or stable) then no hematologic requirements are required to start cycle
 - Treatment
 - Decitabine 20 mg/m² IV daily over 60 minutes (+/- 15 minutes) x 5 consecutive doses on **days 1-5** every 4 weeks given per institutional guidelines
 - **Pre-medication prior to chemotherapy:** per institutional standards
 - Ipilimumab IV (per dose level as in table above) on **day 1** over 90 minutes (+/- 15 minutes) every **8 weeks** for a total of 4 doses during maintenance
 - Decitabine will be dosed prior to ipilimumab on day 1
 - Vitals signs will be repeated hourly from time of ipilimumab infusion for up to one hour after infusion ends (+/- 30 minutes) on day 1.
 - Clinic visits (including physical exam, medication review, ECOG and AE review)
 - Cycles 5-12: on day 1 (+/- 3 days).
 - Procedures:
 - Labs
 - Cycles 5-12: on day 1 (+/- 3 days).
 - At the end of cycles 7 and 10 on a day between days 24-28 and at end of study on a day between days 24-28.
 - Bone marrow biopsy (including aspirate (if aspirable), core, flow cytometry, cytogenetics) will be at the end of cycles 7, 10 and at end of study (on a day between days 24-28) for response assessment.
 - Correlative studies: peripheral blood and aspirate collection at the end of cycles 7 and 10 on a day between days 24-28 and at the end of study (see correlative calendar in [section 10.2](#)).

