 - At the time of response assessments, patients with evidence of disease progression will come off study unless they have evidence of clinical benefit (i.e. improvement in transfusion frequency or peripheral blast reduction). Patients with evidence of disease progression may be allowed to stay on study if deriving clinical benefit with approval from the overall PI as there may be a delayed response with immunotherapy.
 - Additional maintenance dosing (following the same schedule of ipilimumab dosed on day 1 every other cycle with monthly decitabine) for patients with clinical benefit at completion of maintenance therapy will be considered with Overall PI until progression or unacceptable toxicity.

Regimen Description					
Agent	Premedications; Precautions	Dose	Route	Schedule	Cycle Length
Decitabine	Anti-emetic agent per institutional guidelines (i.e. compazine 10 mg injection or equivalent as slow push at a rate not to exceed 5 mg/min per institutional standards given 30 minutes [+/- 15 minutes] prior to chemotherapy)	20 mg/m ² (reconstituted and mixed per institutional guidelines)	Recommend giving decitabine first prior to ipilimumab. IV over 60 minutes [+/- 15 minutes].	Days 1-5 every 4 weeks	
Ipilimumab	None unless history of prior reaction Please see section 6.3 for recommendations for hypersensitivity precautions	1, 3 (starting dose level), 5, or 10 mg/kg	IV over 90 minutes (not bolus or IV push) [+/- 15 minutes]. Administer after decitabine infusion is completed (any time within four hours after infusion completion).	Day 1* every 4 weeks during induction and every 8 weeks during maintenance	28 days (4 weeks)

*Ipilimumab does not start until cycle 1

Please also refer to [section 6](#) for dose delay guidelines.

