Ipilimumab is expected to trigger immune-mediated responses, which require activation of the immune system prior to the observation of clinical responses. Such immune activation may take weeks to months to be evident. For patients with a mass, some patients may have objective volume increase of tumor lesions or other disease parameters (based on study indication, i.e., hematologic malignancies) within (specific 12-24) weeks following the start of ipilimumab dosing. Such patients may not have had sufficient time to develop the required immune activation or, in some patients, tumor volume or other disease parameter increases may represent infiltration of lymphocytes into the original tumor or blood. In conventional studies, such tumor volume or relevant laboratory parameter increases during the first 12 weeks of the study would constitute disease progression and lead to discontinuation of imaging to detect response, thus disregarding the potential for subsequent immune-mediated clinical response. For the purposes of this clinical trial with AML and MDS, patients with sole extramedullary disease with evidence of tumor progression by PET imaging at the end of cycle 2 but without rapid clinical deterioration or change in performance status who do not require additional immediate therapy, may continue to be treated with ipilimumab and clinically observed until the next response evaluation (in this scenario, would then consider repeating a PET scan at the end of cycle 2) to allow detection of a subsequent tumor response.

The reason(s) for protocol therapy discontinuation, the reason(s) for study removal, and the corresponding dates must be documented in the Case Report Form (CRF).

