11.1 Antitumor Effect – Hematologic Tumors

Please see [Appendix D](#) for IWG Response Criteria for AML [6]. Disease progression will be determined by European LeukemiaNet 2017 criteria (Appendix H).

Please see [Appendix E](#) for IWG Response Criteria for MDS [7].

Bone marrow biopsy and aspirate will be performed at screening (will serve as baseline) and end of cycles 1, 2 and 4, and every 3 cycles thereafter (end of cycles 7 and 10). If there is evidence or clinical concern for disease progression, then a bone marrow biopsy and aspirate will be

collected. At each evaluation the patient should have aspirate (if aspirable), cytogenetics and flow cytometry performed. Genotyping will be performed as a part of study correlates.

Hematologic evaluations will be performed with CBC with differential at a minimum of once per cycle. Response assessments may be determined by labs (CBC with differential, particularly platelet count and absolute neutrophil count) within 2 weeks of a bone marrow biopsy as long as it is obtained prior to day 1 of the next cycle.

The best overall response is the best response recorded from the start of the treatment until disease progression/recurrence.

- For those with AML: Best overall response including CR and CRI will be recorded. Patients may remain on study if they have evidence of clinical benefit, stable disease, partial remission, complete remission or complete remission with incomplete count recovery.
- For those with MDS: Best overall response rate will include CR, marrow CR, PR, and hematologic improvement.

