13.5 Analysis of Secondary Endpoints

Safety analyses will be based on the safety population, defined as all enrolled patients receiving at least 1 dose of ipilimumab. Categorical data will be presented as frequencies and percentages. All tests of treatment effects will be conducted at a 2-sided alpha level of 0.05, unless otherwise stated. All tests of interactions will be conducted at a 2-sided alpha level of 0.1, and all CIs will be given at a 2-sided 95% level, unless otherwise stated. Patients who are registered to the study and have received at least one dose of ipilimumab on study will be evaluable for response.

Clinical response to treatment will be assessed following the 2003 IWG criteria for AML [6] and the 2006 IWG criteria for MDS [7]. Anti-leukemic activity will be described in terms of best overall response rate (for AML, to include CR+CRi; for MDS, to include CR+marrow CR+PR+HI), PFS, OS, and remission duration. Time to event summaries will use the Kaplan-Meier method. We will separately evaluate the incidence of acute GVHD and chronic GVHD in patients in the post-allo-HCT cohort, and compare these events with response to treatment.

The focus of this trial is to establish the safety and RP2D of the combination; thus the biomarker studies should be considered exploratory. We will evaluate whether or not absolute lymphocyte count can predict for response for patients who receive combination treatment. ALC levels will be divided into: low (<1000 cells/ul) and normal/high (greater than or equal to 1000 cells/ul). We will compare the response and overall survival of patients with low ALC versus normal/high ALC using Kaplan-Meier estimates and differences will be assessed using log-rank test. We will further capture the absolute change in ALC level measured at baseline to end of cycle 2 (collected prior to dosing on cycle 3 day 1) for response and survival differences. For correlative laboratory tests, we will compare nonrandom measurements in an individual patient either across time (pre-treatment versus on-treatment) with a paired Student *t* test. OS will be censored at the date of last contacts.

REFERENCES

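### Selected patients may continue after progression in case a delayed response occurs, but best overall response closes at progression, so such a response is counted as a non-response.

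*Combined protocol and SAP*

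**What the plan says.** **Continuing after progression.** In Section 5.1 removal is the default. In maintenance, "patients with evidence of disease progression will come off study unless they have evidence of clinical benefit"; the induction text also asks for tolerability. The exception is that patients with progression "may be allowed to stay on study if deriving clinical benefit with approval from the overall PI as there may be a delayed response". Section 5.5 adds a second route for sole extramedullary disease. After PET progression at the end of cycle 2, without rapid deterioration, a change in performance status or a need for other immediate therapy, ipilimumab may continue to the next evaluation "to allow detection of a subsequent tumor response".

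**Counting response.** Section 11.1 states: "The best overall response is the best response recorded from the start of the treatment until disease progression/recurrence". Section 13.5 states: "Anti-leukemic activity will be described in terms of best overall response rate", with CR+CRi for AML and CR, marrow CR, PR or HI for MDS, alongside PFS, OS and remission duration. Section 13.1 uses the same rate at the MTD/RP2D with 90% exact intervals. Under Section 13.5, every registered patient with at least one ipilimumab dose is evaluable for response.

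**Background.** Section 2.2.1 cautions, from melanoma studies, that an "initial determination of progressive disease and consequently PFS may not capture all patterns response and may underestimate the clinical activity of ipilimumab". The immune-related criteria text in Section 2.2.1 asks for standard response definitions as the primary end point and lets immune-related criteria be added as secondary ones. It also offers a separate delayed label for late outcomes, in a sentence that begins: "Patients who demonstrate mixed responses, stable disease, or objective responses by standard RECIST following initial progression may be identified separately as". Sections 11 and 13 do not take up either option.

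**The concern.** The plan gives delayed response as the reason for treating some patients past progression, and then defines its only response measure so that such a response falls outside it. This is a stated rule working against a stated purpose, not a missing detail.

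Two uses of the data are exposed. Section 1 makes preliminary efficacy, with safety and tolerability, a condition for a later phase 2 trial, and the response rate is the main short-term measure of it. The exploratory work also compares responders with non-responders: lymphocyte count and leukemic genotype (Section 1.3), several of the Section 9.3 assays, and GVHD against response (Section 13.5). A patient with a late remission would sit in the non-responder group of each, although that patient shows the pattern the trial kept them on treatment to observe.

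**Working it through.** **1. Trace one patient through the text.** An AML patient meets ELN 2017 progression at the end of cycle 2, has clinical benefit, is approved to stay, and reaches CR at the scheduled end-of-cycle-4 marrow.
- Section 5.1: continuation is permitted, with delayed response as the stated reason.
- Section 11.1: the best-response window closed at the end of cycle 2, so the later CR lies outside it.
- Section 13.5: the patient has had ipilimumab and is in the denominator.
- Result: one patient in the denominator, none in the numerator. Had CR or CRi come before progression, the patient would already count and nothing would change.

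**2. Reproduce the plan's own precision.** Section 13.1 gives 6+6 = 12 or 6+12 = 18 patients at the MTD/RP2D, with 90% exact intervals within ±25% and ±21%. For x responders in n, the Clopper–Pearson limits are:
- lower = Beta⁻¹(0.05; x, n−x+1)
- upper = Beta⁻¹(0.95; x+1, n−x)

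The widest intervals are:
- 6/12: 24.5% to 75.5%, half-width (75.5 − 24.5)/2 = 25.5 points (stated 25).
- 9/18: 29.1% to 70.9%, half-width (70.9 − 29.1)/2 = 20.9 points (stated 21).

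The stated figures reproduce as half-widths, to within rounding or half a point. They do not depend on this concern.

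**3. Effect per patient.** If d patients respond first after progression, the reported rate is lower by d/n than a rate that counts them.

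| d | n=12 | n=18 |
|---|---|---|
| 0 | 0 | 0 |
| 1 | 1/12 = 8.3 points | 1/18 = 5.6 points |
| 2 | 2/12 = 16.7 points | 2/18 = 11.1 points |

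**4. Illustration with one such patient** (the starting counts are assumed):
- n=12: 3/12 = 25% (90% CI 7% to 53%) becomes 4/12 = 33% (12% to 61%).
- n=18: 5/18 = 28% (12% to 50%) becomes 6/18 = 33% (16% to 55%).

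**5. What cannot be computed.** The documents give neither the number of patients who will progress and be kept on, nor a delayed-response rate for AML or MDS. The expected value of d is unknown.

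**The case against.** The strongest reply is that the definition is deliberate. Section 2.2.1 asks for standard definitions as the primary end point and makes immune-related criteria and delayed labels optional. Best response up to progression is a standard quantity. This stands, and it is why the main definition should stay. It does not explain why the permitted separate label was left out of Sections 11 and 13 when Section 5.1 relies on delayed response.

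Other parts of the reply also stand:
- Removal is the default and continuation a conditional exception. A reader might infer that progressing patients are generally kept on; the text does not say so.
- Nothing forbids describing a late response, and Section 1.2.1 aims to observe and record activity. But without a rule, the choice would be made after the data are seen, in a small open-label trial.
- Section 5.5 asks for discussion before removal on radiographic progression, so some apparent progression may never be recorded as such.
- One patient's effect is small beside intervals of about ±21 to ±25 points, and Section 13.5 calls the biomarker work exploratory.
- A late response need not be due to ipilimumab. Section 2.3 gives 2 to 4 cycles as the median time to best response for decitabine alone, and Section 6.5 allows hydroxyurea and, in select cases, palliative radiation.

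A reader might also apply the 10–20% delayed-response figure in Section 2.2.1 to obtain an expected loss. The documents do not support that. The figure is for melanoma, and the same section reports no experience with combinations or other diseases.

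**Conclusion.** The conflict is real but limited. As written, a response first documented after progression enters the best overall response rate as a non-response. The rate may be understated, and such patients may be misplaced in responder/non-responder comparisons. Relative to a rate that counts late responses, any shift is downward: 8.3 points per patient at n=12, 5.6 points at n=18, and zero if no late response occurs. These figures assume the planned MTD/RP2D group sizes and nothing about frequency.

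Two stronger readings go too far. One is that activity is understated: that depends on late responses occurring, and the documents give no rate for this setting. The other is that late responses can never be counted: that is true of the best overall response rate only, because separate labelling is permitted and OS runs on past progression. The MTD/RP2D decision rests on DLTs and is untouched. The melanoma sentence in Section 2.2.1 is background on PFS and sets no endpoint here; the conflict lies between Section 11.1 and Sections 5.1 and 5.5. This is a worthwhile, inexpensive improvement to a secondary endpoint.

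**What to change.** Keep best overall response up to first progression as the main definition, and leave PFS unchanged. State in Section 11.1 which criteria close the window: ELN 2017 (Appendix H) for AML, which Section 11.1 already names although Appendix D carries a different definition of progressive disease, and IWG 2006 (Appendix E) for MDS.

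Add to Sections 11.1 and 13.5:
- A delayed-response category: AML CR/CRi, or MDS CR, marrow CR, PR or HI, first met after documented progression, while on protocol therapy and before any new anti-leukemic therapy. Note any hydroxyurea or palliative radiation.
- The count of such responses with an exact confidence interval (90%, as Section 13.1 uses for response), and the number of patients treated beyond progression.
- The response rate with and without these patients, per arm.
- A repeat of the exploratory responder/non-responder comparisons with these patients as responders, as a sensitivity analysis only.

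The cost is a few lines of text and an extra row in the response table. No new assessments are needed, because marrow evaluations are already scheduled for patients who continue. The downside is that two response figures are reported, and the second cannot be attributed to ipilimumab alone.

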2.3 Decitabine

Decitabine (Dacogen) is an FDA-approved drug for the treatment of MDS. The information below is gathered from the FDA package label. Please see package insert for more details. Dacogen is indicated for treatment of patients with myelodysplastic syndromes (MDS) including previously treated and untreated, *de novo* and secondary MDS of all French-American-British subtypes (refractory anemia, refractory anemia with ringed sideroblasts, refractory anemia with excess blasts, refractory anemia with excess blasts in transformation, and chronic myelomonocytic leukemia) and intermediate-1, intermediate-2, and high-risk International Prognostic Scoring System groups.

Mechanism of Action

Decitabine is believed to exert its antineoplastic effects after phosphorylation and direct incorporation into DNA and inhibition of DNA methyltransferase, causing hypomethylation of DNA and cellular differentiation or apoptosis. Decitabine inhibits DNA methylation *in vitro*, which is achieved at concentrations that do not cause major suppression of DNA synthesis. Decitabine-induced hypomethylation in neoplastic cells may restore normal function to genes that are critical for the control of cellular differentiation and proliferation. In rapidly dividing cells, the cytotoxicity of decitabine may also be attributed to the formation of covalent adducts between DNA methyltransferase and decitabine incorporated into DNA. Nonproliferating cells are relatively insensitive to decitabine.

Pharmacokinetics

Pharmacokinetic parameters were evaluated in patients. Eleven patients received 20 mg/m² infused over 1 hour intravenously (treatment Option 2), fourteen patients received 15 mg/m² infused over 3 hours (treatment Option 1). Plasma concentration-time profiles after discontinuation of infusion showed a biexponential decline. The CL of decitabine was higher following treatment Option 2. Upon repeat doses there was no systemic accumulation of decitabine or any changes in PK parameters. Population PK analysis (N=35) showed that the cumulative AUC per cycle for treatment Option 2 was 2.3-fold lower than the cumulative AUC per cycle following treatment Option 1.

Pharmacodynamics

Decitabine has been shown to induce hypomethylation both *in vitro* and *in vivo*. However, there have been no studies of decitabine induced hypomethylation and pharmacokinetic parameters.

Major route of elimination

The exact route of elimination and metabolic fate of decitabine is not known in humans. One of the pathways of elimination of decitabine appears to be deamination by cytidine deaminase found principally in the liver but also in granulocytes, intestinal epithelium and whole blood.

Metabolism

Drug interaction studies with decitabine have not been conducted. *In vitro* studies in human liver microsomes suggest that decitabine is unlikely to inhibit or induce cytochrome P450 enzymes. *In vitro* metabolism studies have suggested that decitabine is not a substrate for human liver cytochrome P450 enzymes. As plasma protein binding of decitabine is negligible (<1%), interactions due to displacement of more highly protein bound drugs from plasma proteins are not expected.

NONCLINICAL TOXICOLOGY

Carcinogenesis, Mutagenesis and Impairment of Fertility

Carcinogenicity studies with decitabine have not been conducted. The mutagenic potential of decitabine was tested in several *in vitro* and *in vivo* systems. Decitabine increased mutation frequency in L5178Y mouse lymphoma cells, and mutations were produced in an *Escherichia coli lac-I* transgene in colonic DNA of decitabine-treated mice. Decitabine caused chromosomal rearrangements in larvae of fruit flies. The effect of decitabine on postnatal development and reproductive capacity was evaluated in mice administered a single 3 mg/m² IP injection (approximately 7% the recommended daily clinical dose) on day 10 of gestation. Body weights of males and females exposed *in utero* to decitabine were significantly reduced relative to controls at all postnatal time points. No consistent effect on fertility was seen when female mice exposed *in utero* were mated to untreated males. Untreated females mated to males exposed *in utero* showed decreased fertility at 3 and 5 months of age (36% and 0% pregnancy rate, respectively). In male mice given IP injections of 0.15, 0.3 or 0.45 mg/m² decitabine (approximately 0.3% to 1% the recommended clinical dose) 3 times a week for 7 weeks, decitabine did not affect survival, body weight gain or hematological measures (hemoglobin and WBC counts). Testes weights were reduced, abnormal histology was observed and significant decreases in sperm number were found at doses \geq 0.3 mg/m². In females mated to males dosed with \geq 0.3 mg/m² decitabine, pregnancy rate was reduced and pre-implantation loss was significantly increased.

Clinical activity in AML

Decitabine is a well-tolerated DNA-hypomethylating agent that induces differentiation and cytotoxicity of leukemic cells. CR rates from phase 2 and 3 AML clinical trials with front-line decitabine range from 18-25% [15].

Rationale for the Proposed Starting Dose and Dose Escalation Scheme in this Trial

The optimal dosing schedule for ipilimumab in hematologic malignancies is not entirely clear. Studies thus far have mimicked scheduled based on solid tumors (primarily melanoma studies). Ipilimumab is currently approved in unresectable or metastatic melanoma on a 3 week schedule for a total of 4 doses and in the adjuvant melanoma setting on a 3 week schedule for 4 doses (for induction phase) followed by an every 12 week schedule for up to 3 years (for maintenance phase) until disease recurrence or unacceptable toxicity. Ipilimumab has a prolonged half life of ~ 15 days. Dosing during the induction phase on a four week schedule has been previously

evaluated in melanoma in combination with dacarbazine [55] and in B-cell non-Hodgkin lymphoma as monotherapy with evidence of safety and anti-tumor activity [51]. In the Checkmate-012 lung cancer study, multiple schedules of combined nivolumab and ipilimumab were evaluated with similar safety profiles when ipilimumab was dosed on a 3 week versus 6 week versus 12 week schedule. Ipilimumab has been further evaluated in combination with peptide vaccination with a 6 to 8 week schedule with a similar safety profile [56]. Given the highly proliferative nature of AML and the known activity with single agent decitabine (median time to best response 2-4 cycles and median duration of response from 9-14 months) [14, 15], we will shorten the interval between doses in the maintenance phase for ipilimumab from 12 weeks to 8 weeks.

This study will have two arms (cohorts) to the study separated by transplant status. Arm A will include patients who are post allo-HCT. These include patients who are previously had an allo-HCT of any donor source at any time. Arm B will include patients who are transplant naïve. Both arms A and B will be evaluated at the same three dose escalation levels (and same starting dose level) but as the MTD/RP2D may differ based on transplant status, these two patient cohorts will be evaluated separately for safety and toxicity. There will be three intended phases of this clinical trial (for both Arms A and B): priming, induction phase, and maintenance phase.

- **Priming Phase** (Lead- In): The priming phase includes decitabine alone at 20 mg/m² given daily for 5 consecutive doses starting on days 1-5 on a 28 day cycle to provide priming and disease control. Hypomethylating agents, such as decitabine have been tested in the post allo-HCT setting with evidence of safety and tolerability [57-59] including at the same dose proposed in this study.
- **Induction Phase** (cycles 1-4): Cycles 1 through 4 will include treatment with decitabine 20 mg/m² daily for five consecutive doses on days 1-5 plus ipilimumab (given per dose level) on day 1 on a 28 day cycle. There will be three dose escalation levels tested: 3.0 mg/kg (starting dose), 5.0 mg/kg, and 10.0 mg/kg. There will be a dose de-escalation level provided (1.0 mg/kg). Pharmacokinetic data generated from the initial pilot study demonstrated that higher doses of ipilimumab correlated with increased ipilimumab exposure and that those doses may be sufficient to saturate CTLA-4 binding sites [5]. The starting dose level of 3.0 mg/kg was tested in the phase 1b study for relapsed hematologic malignancies after allo-HCT with demonstration of safety and tolerability [4]. There was evidence of preliminary clinical activity (discussed in Section 2.4 in detail) in this study at 10 mg/kg but with evidence of immune related adverse events and GVHD in some cases. Thus we will also test the dose of 5.0 mg/kg.
- **Maintenance Phase** (cycles 5-12): Cycles 5 through 12 will include treatment with decitabine 20 mg/m² daily for five consecutive doses on days 1-5 on a 28 day cycle. Ipilimumab will continue on day 1 every 8 weeks for a total of 4 doses.

